Step 11: Participants will receive counselling on the risks and benefits of PrEP. Following the counseling they will be asked: “Do you want to start taking PrEP today to prevent HIV? You will need to take it daily for it to be effective.” Her response will be recorded.

If yes:

1. The nurse will provide the participant with a 1-month supply of TDF-FTC and invite her to return in 1 month for her next study visit.
2. Nurses will provide contact information to the participant and ask her to call to report any side effects or adverse events while on PrEP, and nurse will track and report serious adverse events to study PIs, Pediatrician, and Obstetrician to decide on how to treat women and infants who have adverse events.

If she says she does not want to start PrEP, woman will be in the deferred PrEP arm:

1. The nurse will schedule her to return in 1 month for the follow-up visit

Step 12: Participants will receive study staff contact information, instructions to call with any questions, and will be scheduled for their next visit in 1 month for the next study visit

Step 13: Participants will receive study staff contact information, instructions to call with any questions, and will be scheduled for their next visit in 1-week to return when test results have returned from the laboratory

Step 14: The study counselor will provide the mother with an appointment card and invitation for her partner to return to receive couples’ HIV testing and counseling (if in a relationship). The session will end by encouraging the client to implement her/his risk-reduction plan (including PrEP if applicable and consistent condom use, couples testing) to prevent HIV acquisition.

Step 15: The participant will receive up to R250 per visit including reimbursement for the participant’s time, transportation and including their refreshments during the study. Further, we will combine the study visits with existing ANC or post-partum/well-baby visits to minimize the travel to the facilities outside of normal clinical checkups.

2. For follow up return visits:

Follow up visits will be monthly until birth (to coincide with ANC visits) then every two months after birth (to coincide with post-partum, well-baby visits).

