Step 1: In ANC: Healthcare providers provide counseling on HIV prevention and treatment at each ANC visit including HIV testing, as part of standard of care. In post-natal care and well-baby visits women may not receive regular HIV testing and messages and will receive this within step 2 (with study counselor). Following their ANC visit, enrolled women will be invited to attend the study site in each MOU to do the follow-up visit including the ACASI survey and prescription and adherence counseling (if on PrEP).

Step 2: ACASI survey at each visit in a private study room

Step 3: In the study room, the study counselors will provide PrEP-specific counseling including adherence counseling for those on PrEP (and management of side effects), or counseling about the risks and benefits of PrEP for women not yet on PrEP. Women not on PrEP will be asked if they are interested in starting PrEP at this visit.

Step 4: STI testing: At 3rd trimester visit and first postpartum visit, participants self-collect a vaginal swab for STI testing (chlamydia, gonorrhea and trichomonas vaginalis using Cepheid® point of care testing). Participants will be treated if diagnosed with a STI according to National Guidelines. They will receive a partner notification letter to bring their partner in for treatment as well.

Step 5 (for women on PrEP): At each visit the study counselor will ask, and record responses, all participants on PrEP about any side effects associated with TDF/FTC, including diarrhea, nausea, fatigue, headache and rash (which are seen in about 10% of participants during the initiation of therapy). We will encourage participants to contact the study nurse if they experience side effects between visits.

For participants on PrEP, the study nurse performs a blood draw for creatinine clearance and a finger prick for DBS testing for adherence measures and (if applicable for this visit). See Table 1 for study calendar.

Step 6: PrEP provision (for 1 or 2 months) and appointment reminder

Follow-up & retention: Tracing information will be taken at the enrolment visit and updated at each study visit. Retention activities will focus on scheduled measurement visits. Following our established approach in this setting, we will provide reminder calls to participants before their measurement visits, and initiate tracing, including home visits, for women who do not attend the measurement visit within one week of the scheduled visit.

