 - If a woman seroconverts while on PrEP, there may be a risk of ART resistance, though research has demonstrated that the risk of ART resistance is very low [12, 13]. In the case of seroconversion, Drs [name] and [name] will follow seroconverters with the study team to evaluate if the patient achieves viral suppression within 6 months of ART start, and if not, she will be referred for specialist attention for testing for ART resistance and clinical follow-up.

Adverse events:

- **Maternal adverse events:** We will collect data on maternal adverse events by asking mothers about intercurrent medical events, which will be reviewed by an obstetrician, including any hospitalizations or illnesses. We will also track and report changes in creatinine or other toxicities in women on PrEP.
- **Infant adverse events:** We will collect data on infant adverse events by asking mothers about infant health or intercurrent medical events, which will be reviewed by a pediatrician.
 - Adverse birth outcomes will include infants that were small for gestational age, pre-term births, miscarriage and stillbirths.

Table 1: PrEP-PP cohort measures by participant study month

Participant study month	Pregnancy						Post-partum											
	1	2	3	4	5	6	7	8	9	10	11	12	13	14	15	16	17	18
Study enrollment and consent of consecutive sample of HIV-negative pregnant women (N=220)	X																	
PrEP group, individual (or couples counseling where applicable) and information, education, counseling materials on PrEP in pregnancy and breastfeeding in local languages (at each visit)	X	X	X	X	X	X	X		X		X		X		X			X
Routine ANC and postnatal care, well-baby visit follow-up (as available in standard of care), including rapid HIV testing, pregnancy, and birth outcomes	X	X	X	X	X	X	X		X		X		X		X			X
ACASI survey to collect: behavioral acceptability, knowledge, and substance use data	X	X	X	X	X	X	X		X		X		X		X			X
Screening at enrolment for Hepatitis B surface antigen. If HBsAg+ = excluded from study	X																	
Laboratory testing for STIs (chlamydia and gonorrhoea) & treatment if positive	X				X		X											
For women on PrEP:																		
Laboratory tests of creatinine (if eGFR<60ml/min cannot continue on PrEP, refer to return in 1 month for re-test)	X			X			X								X			X
PrEP pharmacy refills and adherence supportive counseling monthly (for first 3 months on PrEP) then every 2 months for following months	X	X	X		X		X		X		X		X		X			X

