DBS taken for TDF-DP adherence measures (bi-monthly in participants on PrEP)	X	X	X		X		X		X		X		X		X			X
In-depth interviews for 20 participants							X											X
Collect study data on: (1) PrEP counseling, (2) PrEP medication when requested, (3) regular appointments, (4) IEC materials, (5) adherence counselling and support by facility, through patient ACASI survey at every study visit	X	X	X	X	X	X	X	X	X	X	X	X	X	X	X	X	X	X

Training, quality assurance and supervision:

1. *Existing DOH staff:* We will conduct an on-site half day training for existing counselors, nurses and midwives and Managers in the two study sites on the study protocol to ensure that they understand and support the integration of the study in their facility.

- a. **Inclusion of interviews for healthcare providers in health facility to understand their knowledge of and attitudes around PrEP:** We seek to interview existing health care providers including nurses, counselors, midwives and managers to understand their knowledge about PrEP, HIV prevention in pregnancy and any attitudes about PrEP that may affect future integration of

PrEP and PrEP uptake in the facility. We will interview approximately 20 health care providers and have one focus group in those providers in isiXhosa or Afrikaans. We will record, translate and transcribe their responses and analyze the results thematically in order to develop interventions around provider training and support.

2. *Study staff:* We will hire 2 counselors, 2 nurses, 2 coordinators who will receive a 3-day training program and they will be required to complete the entire training course. After completion of the training, the study PI will observe the counselor and nurse completing each step of the intervention with a mock patient. Upon satisfactory completion of observed sessions, the counselors and nurses will be certified to conduct the study intervention and will receive a completion certificate.
3. *Quality assurance* will occur on three levels. Day-to-day monitoring, supervision, and support of counselors will be carried out by the Study Coordinators (from UCT—1 per facility). The Study Coordinator will provide on the job training to ensure that counselors and nurses respect the study protocol. Adherence to the counseling protocol will be established by the Study Coordinator who will sit in on a random subsample of 20% of counseling sessions to ensure that counselors are adhering to study protocols.

Sources of data

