There are four sources of data/materials for this trial: (1) survey measures (ACASI); (2) in-depth interview measures in 20 randomly selected women (n=10 who were on PrEP compared with 10 not on PrEP); (3) laboratory measures; and (4) information abstracted from routine care records, including related to PrEP. The collection of data materials will be conducted by a study measurement team comprised of one study coordinator, one study interviewer, and one fieldworker. All procedures for data collection (regardless of source) will be outlined in a study manual of procedures, with individual activities guided by standard operating procedures (e.g., DBS, specimen transport, or questionnaire administration).

Survey measures (ACASI)

At study measurement visits, questionnaires will be administered to mothers participating in the study using ACASI on a tablet with a site coordinator available for troubleshooting. ACASI will help reduce the amount of respondent bias when responding to sensitive questions around sex and substance use. Following standard procedures, the questionnaires will be translated into isiXhosa and Afrikaans and back translated to ensure appropriate phrasing. Questionnaires will include:

- Basic demographic information and obstetric history (enrollment only)
- Partner's HIV status
- Sexual behaviors in the past month and week including # of sex partners, type of sex, and frequency of sex and condom use
- Substance use information using the AUDIT-C and DAUDIT scales
- Risk perception scales
- Partner, community and social support for PrEP
- For PrEP users, questions related to PrEP adherence according to self-report (the 3-day and 1-month recall and a visual analog scale) and pharmacy-based pill counts will be conducted at each study measurement visit.
- Additional schedules will be used to collect data on symptoms in mothers that are potential side-effects of PrEP use (at all study visits)
- We will also use short questionnaires to collect data on all women's experiences in the study, and the acceptability of the PrEP initiation, including what kind of services were offered at each visit (e.g. counseling, peer mentorship, and IEC materials, medication)
- Self-reported symptoms related to STIs

- This will focus on the positive and negative aspects of their experiences of PrEP initiation in pregnancy and breastfeeding and any factors associated with PrEP initiation, retention, and adherence.

Interview measures

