The primary analysis will focus on measuring the distribution of women across the PrEP cascade including: initiation, retention and adherence. **PrEP initiation** will be based on a woman’s uptake of PrEP and allow for stoppage and re-initiation; **PrEP retention** will be defined as not missing >1 visit among those on PrEP (with separate analyses of PrEP stoppage). For **PrEP adherence** for women on PrEP we will measure both **perfect adherence** (i.e. level of objective adherence throughout pregnancy and breastfeeding periods) as well as “**prevention-effective**” adherence (i.e. adherence before and during times of sexual activity) in participants through objective and subjective measures to evaluate agreement between the two measures, and the level of under- or over-reporting. Primary adherence analyses will use objective measures (TDF-DP from DBS) taken on all those who enrolled and initiated PrEP; subsidiary analyses will consider (i) other adherence measures and (ii) multiple imputation for missing adherence data.

- **Use of PrEP will be measured** through alternate definitions of the main outcomes (e.g. adherence by self-report versus adherence by pharmacy refill), compared using measures of agreement and will be analyzed as independent models to contrast estimated associations.

- **Measurement of prevention-effective execution:** Execution refers to PrEP adherence during a time when at-risk sex happens. It is calculated by: number of doses reported, or recorded/number of expected doses based on HIV risk and PrEP initiation/discontinuation
- **Prevention-effective continuation:** Prevention-effective continuation describes the duration of PrEP use during periods of HIV risk and references the absolute time of use during pregnancy and breastfeeding periods. We will adapt the methodology from previous PrEP studies in SA including FEM-PrEP to create a semi-ordinal composite adherence score from blood specimens from DBS every 2-months.

Table 2: Study measures for PrEP-PP

Primary Outcomes	Measurement	Source	Frequency
PrEP initiation	# of women who initiate PrEP over time / total # of women in active cohort = proportion of women who initiate PrEP	Electronic provider log (REDCap)	Daily entry, weekly analysis

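### Sexual behaviour is recalled over one month at most, so with postpartum visits two or three months apart, at-risk sex goes unasked for about half of the postpartum year

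*Combined protocol and SAP*

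**What the plan says.** Under Sources of data, Survey measures (ACASI), the questionnaire content includes "Sexual behaviors in the past month and week including # of sex partners, type of sex, and frequency of sex", together with condom use. The same list gives 3-day and 1-month recall, a visual analogue scale and pill counts for pill-taking. The DBS paragraph in section 5 adds a since-last-visit recall, but only for PrEP adherence.

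On timing, the follow-up procedures in section 5 specify an "ACASI survey at each visit in a private study room" and state: "Follow up visits will be monthly until birth (to coincide with ANC visits) then every two months after birth". In Table 1, the row "ACASI survey to collect: behavioral acceptability, knowledge, and substance use data" is marked at months 1 to 6 in pregnancy and at months 7, 9, 11, 13, 15 and 18 postpartum.

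On use of the data, section 6 defines prevention-effective adherence by reference to when the woman is sexually active. Execution is "number of doses reported, or recorded/number of expected doses based on HIV risk and PrEP initiation/discontinuation". Continuation is how long PrEP is used while the woman is at risk, across both pregnancy and breastfeeding. Table 2 lists subjective adherence as a primary outcome and ties it to periods of sexual risk.

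**The concern.** Execution, continuation and subjective adherence all need the woman's risk status throughout each interval between visits. After birth, the survey reaches back one month into an interval of two or three.

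This also sets up a mismatch between numerator and denominator. PrEP is dispensed every two months after the first three months, so pill counts, refill records and since-last-visit pill recall can span the whole interval, while risk is known only for its last month. The plan does not say how the remaining weeks are to be classified. Its multiple imputation is for missing adherence data, not for risk time that was never asked about.

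No other scheduled measure dates exposure later on: STI testing stops at the first postpartum visit. Timing matters because the plan allows women to stop and restart PrEP. A study meant to supply cascade estimates would then report late-postpartum adherence on an unstated assumption about risk, and a larger sample would not cure that.

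**Working it through.** The plan gives no figure for the share of risk time covered, so there is none to reproduce. The check is interval arithmetic.

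**Inputs**
- Recall window: 1 month (the past week lies inside it), from Survey measures (ACASI).
- Survey months: 1, 2, 3, 4, 5, 6, 7, 9, 11, 13, 15, 18, from the ACASI row of Table 1, with birth at month 6.
- Follow-up: 18 months, 6 in pregnancy and 12 postpartum, as in Table 1.

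**Formula**

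Unseen share = sum of max(0, gap − recall window) ÷ sum of gaps.

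**Table 1 schedule**
- Gaps from month 6: 1, 2, 2, 2, 2, 3. Unseen: 0 + 1 + 1 + 1 + 1 + 2 = 6 months.
- Postpartum year (months 6 to 18): 6/12 = 50.0%.
- Whole follow-up: 6/18 = 33.3%, or 6/17 = 35.3% counted from the enrolment visit.
- First postpartum visit to the end (months 7 to 18): 6/11 = 54.5%.
- Last interval (months 15 to 18): 2/3 = 66.7%.

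**Strict two-month schedule from the text**
- Visits at months 8, 10, 12, 14, 16, 18: 6/12 = 50.0% from birth, or 5/11 = 45.5% from month 7. Whole follow-up: 6/18 = 33.3%, or 6/17 = 35.3% from enrolment.
- Visits at months 7, 9, 11, 13, 15, 17: 5/11 = 45.5% from birth, or 5/10 = 50.0% from month 7. Whole follow-up: 5/17 = 29.4%, or 5/16 = 31.3% from enrolment.

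**Sensitivity on Table 1**
- If a month is read as 30 days (of 30.4375), the postpartum share is 6.086/12 = 50.7%. At 28 days it is 6.480/12 = 54.0%. The whole-follow-up share becomes about 34% to 40%.
- With k months of antenatal follow-up instead of 6, the overall share is 6/(12 + k): 46% for k = 1, 40% for k = 3, 35% for k = 5.

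**Table 2 objective outcome (third trimester to six weeks postpartum)**
- Months 5 to 7, which hold most of this window: 0/2 = 0% unseen.
- If the window is stretched to the month 9 visit: 1/4 = 25%.

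**After the fix**
- A since-last-visit item leaves 0 of 12 postpartum months unasked between attended visits.

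**The case against.** Four points on the other side have weight.

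- **Size.** A reader might infer that most of the risk time needed for prevention-effective adherence is unseen. The documents do not support that. Continuation covers pregnancy as well as breastfeeding, and antenatal visits are monthly. The 54.5% figure arises only by starting the count at month 7, which drops pregnancy and the fully covered interval from month 6 to 7.
- **Primary result.** A reader might infer that the primary adherence analysis is compromised. Section 6 bases it on drug levels in dried blood spots, and the Table 2 objective outcome falls mostly where visits are monthly. What remains exposed is subjective adherence, which Table 2 still lists as primary.
- **Computability.** A reader might infer that execution cannot be computed after birth. It can, within the recalled month, because 1-month pill recall matches the 1-month sex recall. What is lost is continuous coverage between those samples, mainly for continuation.
- **Bias.** The plan does not say that unasked weeks will be counted as free of risk, so no direction or amount of bias can be claimed. Partner HIV status and risk perception are also collected and can inform risk, though they do not date sex acts.

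Two further replies carry less weight. The last Table 1 row, ending "adherence counselling and support by facility, through patient ACASI survey at every study visit", is marked in all 18 months, and a monthly survey would close the gap. But that row concerns service data and conflicts with the visit rows and the text, so it needs reconciling and cannot be relied on. The questionnaire list may also be a summary, with detail in a manual of procedures; as the plan is written, though, only month and week appear.

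**Conclusion.** The point holds as a measurement gap in later postpartum follow-up. At-risk sex is unasked for about half of the postpartum year (6 of 12 months on Table 1; 45-50% on a strict two-month schedule) and about one third of follow-up (6 of 18 months). It bears on later-postpartum execution and continuation and on the Table 2 subjective outcome, and only slightly on the objective outcome.

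The figures assume that every visit is attended on schedule, that the window is one full month, and that birth falls at month 6. Missed visits would raise the unseen share. They are shares of calendar time; reading them as shares of risk further assumes that risk is even over time, and they are not estimates of bias. The study is a formative pilot, so this is an inexpensive improvement to make before the questionnaires are translated; it does not invalidate the design.

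**What to change.** At every visit, add one ACASI item asking whether any condomless sex has occurred since the last visit and, if so, in which month. State in section 6 that this item defines the risk intervals for continuation, for expected doses in execution, and for subjective adherence. Keep the past-month and past-week items for detail, and report execution restricted to the recalled month as a sensitivity analysis. Reconcile the last Table 1 row with the visit schedule.

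The cost is one or two extra questions to translate and answer. The drawback is that recall over two or three months is less accurate than over one; keeping the shorter items and the restricted analysis shows how far this matters.

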The primary analysis will focus on measuring the distribution of women across the PrEP cascade including: initiation, retention and adherence. **PrEP initiation** will be based on a woman’s uptake of PrEP and allow for stoppage and re-initiation; **PrEP retention** will be defined as not missing >1 visit among those on PrEP (with separate analyses of PrEP stoppage). For **PrEP adherence** for women on PrEP we will measure both **perfect adherence** (i.e. level of objective adherence throughout pregnancy and breastfeeding periods) as well as “**prevention-effective**” adherence (i.e. adherence before and during times of sexual activity) in participants through objective and subjective measures to evaluate agreement between the two measures, and the level of under- or over-reporting. Primary adherence analyses will use objective measures (TDF-DP from DBS) taken on all those who enrolled and initiated PrEP; subsidiary analyses will consider (i) other adherence measures and (ii) multiple imputation for missing adherence data.

- **Use of PrEP will be measured** through alternate definitions of the main outcomes (e.g. adherence by self-report versus adherence by pharmacy refill), compared using measures of agreement and will be analyzed as independent models to contrast estimated associations.

- **Measurement of prevention-effective execution:** Execution refers to PrEP adherence during a time when at-risk sex happens. It is calculated by: number of doses reported, or recorded/number of expected doses based on HIV risk and PrEP initiation/discontinuation
- **Prevention-effective continuation:** Prevention-effective continuation describes the duration of PrEP use during periods of HIV risk and references the absolute time of use during pregnancy and breastfeeding periods. We will adapt the methodology from previous PrEP studies in SA including FEM-PrEP to create a semi-ordinal composite adherence score from blood specimens from DBS every 2-months.

Table 2: Study measures for PrEP-PP

Primary Outcomes	Measurement	Source	Frequency
PrEP initiation	# of women who initiate PrEP over time / total # of women in active cohort = proportion of women who initiate PrEP	Electronic provider log (REDCap)	Daily entry, weekly analysis
PrEP retention	# of women on PrEP who return for study visits (do not miss more than 1 visit) / total # of women in active cohort who are prescribed PrEP= proportion of women on PrEP who are retained in PrEP study	Electronic provider log (REDCap)	Daily, analysis weekly
PrEP adherence-subjective	# of women taking PrEP, who self-report taking their medication daily (& pill count to confirm this) during periods of sexual risk over time / total woman-time on PrEP in active cohort = PrEP adherence rate (subjective)	Electronic provider log (REDCap)	Daily, analysis weekly
PrEP adherence-objective	# of women taking PrEP who have >80% levels at >40ng/mL TDF-DP (indicating dosing in past 24 hours) at 3 rd trimester, delivery, and 6 weeks postpartum (and during sexual risk periods during that time) / total woman-time on PrEP in active cohort = PrEP adherence rate (objective)	Lab analysis of TDF-DP measures	Quarterly
Secondary Outcomes			
Predictors of attrition at key steps in the PrEP cascade	Individual, pill/study and disease specific predictors of attrition	ACASI	ACASI: Every study visit
HIV outcomes	HIV testing data: HIV-uninfected, HIV-positive for mother and child (if mother seroconverts)	Electronic provider log (REDCap)	Every visit
Health outcomes and adverse events	Any side-effects, creatinine, any negative maternal or neonatal outcomes (for mother and infant)	Electronic provider log (REDCap)	During routine lab tests and visits

Each outcome will be described via cumulative incidences at fixed intervals (e.g., cumulative PrEP initiation by delivery) and incidence densities over time. The general statistical approaches to these outcomes are analogous; data will be described graphically, including product-limit graphs, with preliminary analyses based on standard approaches for rates and proportions. The modelling approach will vary depending on the nature of the outcome. **PrEP initiation** will be modelled using a probit model (preferred to estimate risk factors for common outcomes) with individual-level covariates as fixed effects; when time-dependent or visit-specific covariates are included in the analysis of cumulative initiation we will shift to a mixed-effects setting with random effects around individual participants. **PrEP retention** will be examined using similar approaches; in addition, we will use time-to-event methods to estimate factors associated with time to loss (non-retention) among women having initiated PrEP. **PrEP adherence** will be modelled using mixed effects probit models as above and generalized estimating equations to examine the marginal effect of individual-level covariates on adherence during the study [85]. Throughout, robust estimates of standard errors will be used.

The same modelling approaches will be used to explore secondary implementation questions such as the effect of individual, pill/study, and disease factors on PrEP initiation, retention and adherence outcomes (see Figure 1 for conceptual model). The main exposures include: **individual level factors**: risk perception, community/family support, sexual activity, risk, concerns about drug's side effects and harm on self (pregnancy) and/or infant's health. **Pill regimen and study factors** include: PrEP side effects, time required to participate in study, patient-provider relationship measured from the participants' perspective. **Disease factors** include: stigma around HIV and PrEP, and partner's HIV status (see Table 5 for specific variables).

We will also describe the frequency of **HIV outcomes**, including maternal HIV acquisition and MTCT, and any laboratory or self-reported side effects (e.g. changes in creatinine or self-reported side-effects [GI symptoms, headache, and etc.]). Analyses will include pure-count and person-time approaches; for the latter, confidence intervals will be calculated following the method of Breslow and Day [86]. We will also describe **infant outcomes over time** (including birthweight, gestational age at delivery, pregnancy loss and any infant illness, hospitalization or death). While we expect the frequency of adverse HIV-related outcomes to be low, we will describe characteristics of women who did/did not acquire HIV, and consider further analyses using the approaches outlined above.

Qualitative data analysis considerations

Following our standard practice, study tools including in depth interview guides and ACASI materials will be translated into isiXhosa and Afrikaans, the predominant local languages, with independent back-translation for verification. We will digitally record the IDIs and then have the recordings transcribed verbatim. The recordings will be reviewed and verified for accuracy by the interviewers. Transcripts will then be translated and key quotations back-translated to verify meaning. A subset of 20% of transcripts will be double-coded to examine the inter-rater reliability of the coding process. After coding, Investigators will search by substantive codes and themes identified utilizing matrices to organize and allow for comparisons by group (e.g. age, pregnancy stage, partner status, initiators and non-initiators). Patterns in the matrices will be used to identify themes. Tables of themes will be created using the verbatim quotations as evidence to support the themes that serve as the primary data analyses approach. Conclusions will be based on interpretation of these tables of themes with quotations. Data will be managed using NVivo Software (QSR International).

Data management

Data management will take place at the site following procedures established for other research protocols conducted in Gugulethu. Data collected on paper forms will be entered into a custom designed RedCap database, maintained in a firewall-protected UCT server with nightly backups. The study database will be password-protected following standard password safety procedures. The database will be designed and maintained by a senior data manager who will develop the data dictionary, direct queries, and data quality assurance / quality control activities, and will supervise the data entry clerk. Data quality assurance will be in the form of robust database structure and platform, and "front-end" data checks, including real-time database queries. Quality control will be through data checking scripts to identify out-of-range values, logic violations, and missing observations. Data editing will be based on reference to the form and/or source document in question; all data queries and responses will be logged, and edits will be implemented through separate program files. All study records will contain anonymous participant identification numbers, and no participant names or identifiers will be recorded. Patient routine folder numbers will be stored in a separate password protected database. Once all routine data are linked the folder number will be removed and only the study identification number will be used.

7. Ethical considerations

Ethical review

The study protocol, informed consent form, all data collection tools, and other requested documents will be reviewed and approved by the University of Cape Town Faculty of Health Sciences Human Research Ethics Committee (UCT-HREC). After the initial review and approval, UCT-HREC will review progress of the study at least annually. Following the approval, we will submit the protocol and approval to University of California Los Angeles (UCLA) for secondary review and approval. UCLA IRB will also review progress of the study annually and we will report all adverse events or amendments to both Ethics Committees.

Insurance

Currently we propose that this protocol is covered by UCT's no-fault insurance policy as this is non-commercially sponsored interventional research.

Ethics approach for including adolescent girls (16+ years old) in study

As per the Department of Health. Guidelines for Good Practice in the Conduct of Clinical Trials with Human Participants in South Africa [21] we will collect parental or guardian consent to participate in the study as well as assent from the minor.

The risk is justified by the anticipated benefit to the subjects: the risks associated with PrEP-PP study procedures are minor and largely non-invasive (except for phlebotomy) and are justified by the anticipated benefit that PrEP would have on prevention of HIV acquisition in this vulnerable group. Thus, there is the potential for direct benefit associated with participation.

Informed consent

Informed consent for the study and questionnaire is modelled after that used in previous studies and will be delivered in participants' home language (isiXhosa or Afrikaans) by trained interviewers. This ICF details the purpose of the study, study procedures, and the risks and benefits to mothers that participants may encounter at the additional study measurement visit. This consent includes a separate specimen storage section. Participants who do not consent to specimen storage but who consent to the main study visit will still be able to complete the rest of the study.

Here, study staff will emphasize to participants that:

- Participation is entirely voluntary, and their choice regarding participation will in no way influence the quality of routine medical care for mothers or their infants
- Women may exit the study at any time for any reason without compromising the quality of health care received.

English versions of the informed consent documents are provided in the Appendix to this document. Translated isiXhosa and Afrikaans versions (as well as a certification of their translation and back-translation) will be submitted to the HREC before the start of the study.

Risks

The potential risks to participants in the study include:

- Risks associated with collection of self-reported behavioural and psychosocial information, related to psychosocial distress raised by questionnaire items involving social support, mental health, or disclosure of HIV status

- Risks due to loss of confidentiality due to study procedures—for instance, in the process of data collection
- Risk associated with asking participants to disclose their status, and potential for interpersonal violence by the partner resultant from the disclosure.

The potential risks to participants who take PrEP include:

- Risks associated with PrEP side effects (headaches, gastro-intestinal) for women on PrEP
- Risks associated with PrEP adverse events for women on PrEP
- Risks associated with collection of dried blood spots

All participants will be informed of these risks, and the strategies to minimize these, as part of the informed consent process. These strategies draw directly from prior experiences conducting research on HIV prevention and treatment in Gugulethu, Mitchell’s Plain and similar communities across Cape Town.

Benefits

Direct benefit

The major potential direct benefit from participating in this study is that pregnant women will receive best possible HIV prevention including ongoing counseling, Hepatitis B screening, STI testing and treatment and PrEP if they choose to take it which can prevent HIV acquisition during pregnancy and breastfeeding periods. If women do not opt to take PrEP, or are not adherent to PrEP, she will still receive the ongoing counseling and STI testing/treatment. Their participation may help us answer our research questions and help us inform health programs for pregnant women in the future. The benefit of participating in the study and preventing HIV acquisition and onward infant transmission is likely to outweigh the risk of PrEP exposure or other risks.

Indirect benefit

By identifying the optimal strategy for delivering PrEP to pregnant women, this study has the potential to lead to improved HIV prevention interventions to protect against HIV acquisition and vertical transmission in HIV-uninfected women and their infants in Cape Town, the Western Cape Province, and across South Africa.

Compensation

Participants will be given up to R250 per visit including reimbursement for the participant’s time, transportation and including their refreshments during the study. Visits will correspond to regular ANC or postpartum/well-baby clinical visits wherever possible. All participants will also receive refreshment on the day of their visit.

Confidentiality

The following steps will be taken to minimize the risk of any loss of confidentiality throughout study design and conduct.

- All personnel involved in data collection and management will undergo specific training for the study in confidentiality and related patient protection issues.
- Following standard practice, all patient- and study-related information will be kept in locked cabinets at either the study office in Gugulethu, Mitchell’s Plain or at UCT.
- Anonymous participant identification numbers will be used on all study documents. Collection of participant names and other identifiers will be restricted to informed consent documents, patient tracing materials, and a study identification key, all of which will be kept in a locked cabinet in the study office at Gugulethu and at UCT separate from other study documentation and accessible only by the project

coordinator and local PI. No CRF will include participant name, including CRF that may reflect HIV status of women or their children (including STI test results or treatment).

- All electronic records will be kept in password-protected files. All electronic communications of study data will be through password-protected, encrypted files. All data storage at the University of Cape Town will be within a firewall-protected server.

While efforts will be made to minimize the loss of confidentiality, in the event that staff learn that the participant is a threat to themselves or to others or of possible abuse by partners, the proper authorities will be notified. This exception will be included in all study informed consent forms.

Internal monitoring

The purpose of monitoring is to verify the rights and well-being of human subjects are protected; that trial data is accurate, complete and verifiable with source data; that the trial is conducted in compliance with the protocol, GCP and the applicable regulatory requirements. Throughout the conduct of the study, internal study monitoring will be led by the study PIs. We are collaborating with the study Paediatrician, [name] and Obstetrician, [name], who will monitor emergent clinical concerns as co-Investigators. They will monitor all adverse events and advise on treatment for all participants who have adverse events.

Throughout the duration of the study, study PIs, co-investigators and the study coordinator will participate in weekly conference calls to monitor the rate of participant enrolment and the integrity of protocol implementation (including the completion of informed consent and quality of study measures). In addition, participant retention and safety endpoints will be discussed as well. We will report all serious maternal and/or infant adverse events, including any laboratory or other measures that require women to stop PrEP, to the study's DSMB and Ethics Committee.

